## **Compliance**

Compliance will be assessed by the investigator and/or study personnel at each patient visit and information provided by the patient and/or caregiver will be captured in the Drug Accountability Form. This information must be captured in the source document at each patient visit.

Patient compliance with study treatment will be evaluated using the pill count. The details of summary of compliance are explained in [Section 2.7.2](#).

### **2.4.2 Prior, concomitant and post therapies**

Prior and concomitant medications will be summarized in separate tables by treatment group.

Prior medications are defined as treatments taken and stopped prior to first dose of study treatment. Any medication given at least once between the day of first dose of randomized study treatment and the date of the last study visit will be a concomitant medication, including those which were started pre-baseline and continued into the period where study treatment is administered.

Medications will be presented in alphabetical order, by Anatomical Therapeutic Classification (ATC) codes and grouped by anatomical main group. Tables will show the overall number and percentage of patients receiving at least one treatment of a particular ATC code and at least one treatment in a particular anatomical main group.

Significant prior and concomitant surgeries and procedures will be summarized by primary system organ class and MedDRA preferred term.

The number and percentage of patients receiving prior and concomitant medication or therapy will be provided by system organ class and preferred term.

Prior or concomitant medication will be identified by comparing recorded or imputed start and end dates of medication taken to the reference start date.

## **2.5 Analysis of the primary objective**

The primary objective of the study is to evaluate patient preference of deferasirox FCT or deferasirox DT at Week 48.

### **2.5.1 Primary endpoint**

The primary endpoint is the proportion (and percentage, %) of patients who claim preference of deferasirox FCT over deferasirox DT as measured by preference questionnaire at Week 48.

The analysis of primary variable will be based on the FAS.

### **2.5.2 Statistical hypothesis, model, and method of analysis**

The null hypothesis is that there is no difference in the proportion of patients preferring FCT or DT at Week 48. The alternative hypothesis is that there is a difference in the proportion of patients preferring FCT or DT at Week 48.

Let  $p_{.1}$  denote the proportion of patients with preference (discordance) or no-preference (concordance) of DT and  $p_{1.}$  denote the proportion of patients with preference or no-preference of FCT, at Week 48.

In statistical terms, the following hypothesis will be tested for primary objective:

$H_1: p_{1.} = p_{.1}$ , versus  $H_{A1}: p_{1.} \neq p_{.1}$

This is equivalent to test:  $H_1: p_{12} = p_{21}$ , versus  $H_{A1}: p_{12} \neq p_{21}$ ,

where  $p_{12}$  and  $p_{21}$  denotes the proportion of patients with preference of FCT over DT and vice versa.

In other words,

$H_1$ : Deferasirox FCT is not different from deferasirox DT with respect to patient preference at Week 48

versus

$H_{A1}$ : Deferasirox FCT is different from deferasirox DT with respect to patient preference at Week 48

The primary analyses of testing patient preference of FCT over DT will be conducted via Mc Nemar's test. Both exact and asymptotic p-values will be presented for Mc Nemar's test for the matched pairs. Along with p-values, the estimates of proportions and percentages (%) of patient preferences and non-preferences for each study treatment will also be presented along with 95% CI (if required) using Clopper-Pearson method. The Type I error will be set to 2-sided  $\alpha=5\%$  or 1-sided  $\alpha=2.5\%$ . The testing will be done on the patients who have completed question 2 in the preference questionnaire.

### **2.5.3 Handling of missing values/censoring/discontinuations**

There will be no imputation for missing data. Wherever appropriate, available data will be summarized over specified intervals using suitable summary statistics.

Patients should be seen for all visits to perform the scheduled assessments on the designated day, or as close to it as possible, i.e., not exceeding  $\pm 2$  days for all assessments scheduled in Visits 1 to 7 and  $\pm 7$  days for all other visits till Visit 777. In this clinical study, a week is 7 calendar days.

### **2.5.4 Supportive analyses**

Sensitivity analyses and supportive analyses will be conducted in order to provide evidence that the results seen from the primary analysis are robust.

In order to support the Mc Nemar's test for matched pair, the Odd's Ratio (OR) of patient preference (i.e.  $OR=p_{12}/p_{21}$ ), 95% CI and p-values will also be presented. Conditional logistic model for matched pair analyses may also be fitted if feasible.

The primary and above supportive analyses will also be performed for each subgroup of the baseline factor, i.e. on patients with TDT or NTDT and also on prior treatment status of iron chelation (naïve or pre-treated). Additionally, the primary analysis will be performed by age groups: 2-6 years (infant), 7-11 years (child), 12-17 years (adolescent), < 18 years (overall of infant, child and adolescent), and  $\geq 18$  years (adult). No p-values will be presented for subgroup analyses.

To identify the impact of preference on switching, the primary analyses will be performed separately for patients with or without switching before Week 48.

As a supportive analysis, the primary analysis will also be provided for PPS.

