4.2 Switching of treatments

At the discretion of the investigator, patients can switch from deferasirox DT to deferasirox FCT at any time during Period 1 of the Core phase, and vice versa, from deferasirox FCT to deferasirox DT at any time during Period 2 of the Core phase.

This change and the rationale of the switch must be recorded in the CRF. Also the investigator must provide the preference questionnaire to the patient at the immediate next visit and then keep following the schedule of questionnaires pre-planned on [Table 7-1](#) and [Table 7-2](#) (for example; if the investigator decides to switch from deferasirox DT to deferasirox FCT at Week 12, the preference questionnaire must be provided to the patient on the next visit, Week 16, and the rest of the preference questionnaires as per regular schedule: Week 24, Week 28 and Week 48). Please refer to [14 Appendices](#) for further information on preference questionnaire completion.

The investigator can decide in the best interest of the patient to switch from one formulation to the other with the agreement of the patient if an adverse event (*defined as the appearance of (or worsening of any pre-existing) undesirable sign(s), symptom(s), or medical condition(s) that occur after patient's signed informed consent has been obtained*) grade ≥ 2 (GI symptoms, skin rash, laboratory abnormalities) occurred with deferasirox DT or deferasirox FCT.

Re-switching treatments is not allowed within each period in this study, which means that a patient cannot switch from Deferasirox DT to Deferasirox FCT and the switch back to Deferasirox DT, and viceversa (Deferasirox FCT to Deferasirox DT, and then back to Deferasirox FCT).

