10.4.4 Supportive and Sensitivity analyses

Sensitivity analyses and supportive analyses will be conducted in order to provide evidence that the results seen from the primary analysis are robust.

In order to support the Mc Nemar's test for matched pair, the Odd's Ratio (OR) of patient preference (i.e., $OR=p_{12}/p_{21}$), 95% confidence interval (CI) and p-values may also be presented, if appropriate. Conditional logistic model for matched pair analyses may also be fitted if required.

The above primary analyses will also be performed for each subgroup of stratification factor, i.e., on patients with transfusion dependent or non-transfusion dependent thalassemia. Also, the primary analyses may be performed based on prior treatment status of iron chelation.

In case of switching, the primary analyses will be performed separately for patients with or without switching before Week 48. Further details will be presented in SAP.

The primary analysis will also be provided for PPS.

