### 3 Sample size calculation

Based on data from the ECLIPSE study (Taher et al 2018), the following assumptions have been made at Week 48, the patient preference for deferasirox FCT (formulation) is 45% and preference for deferasirox DT (formulation) is 25% and no preference to either of the formulations is 30%. This means the discordant pairs is 70 % (i.e. 70% preferred one formulation over another, 45 %) and concordant pairs= 30% (assuming same preference for each formulation, 15%).

At least 130 patients are needed at Week 48 to have 80% power to detect the difference of patient preference of 20% (i.e. 45% preference of FCT over DT and 25% preference of DT over FCT) at a two sided significance level of 0.05 using McNemar's test for matched pairs.

To allow for roughly 10% of subjects with missing measurement, a total of approximately 145 evaluable patients aged  $\geq 2$  years male or female with TDT or NTDT requiring chelation therapy due to iron overload, need to be enrolled. Patients may have been previously treated with iron chelators (other than deferasirox DT) or be chelation-naïve.

EAST 6.0 is used to calculate the sample size.

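### The SAP's switching analysis tests FCT against DT within switchers and within non-switchers, so it cannot answer its stated question about preference and switching (minor, supportive analysis)

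*SAP*

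**What the plan says.** SAP 2.5.4 opens by giving robustness of the primary result as the purpose of the supportive analyses. For switching it then states a narrower purpose: "To identify the impact of preference on switching, the primary analyses will be performed separately for patients with or without switching before Week 48".

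The analysis to be repeated is defined in SAP 2.5.2: "The primary analyses of testing patient preference of FCT over DT will be conducted via Mc Nemar's test". Its null is p12 = p21, that is, as many patients prefer FCT over DT as the reverse. Proportions are reported as well, with Clopper-Pearson intervals if required.

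Protocol 10.4.4 prescribes the same division without any aim about preference and switching: "In case of switching, the primary analyses will be performed separately for patients with or without switching before Week 48". It leaves further detail to the SAP.

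Protocol 4.2 allows both directions: "patients can switch from deferasirox DT to deferasirox FCT at any time during Period 1 of the Core phase, and vice versa". Neither document divides switchers by direction in this analysis. Elsewhere, switching is only described. SAP 2.4.1 summarises counts and reasons, and SAP 2.11 summarises the preference questionnaire given at the visit after a switch.

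The sentence just before the switching sentence in SAP 2.5.4 rules out p-values for subgroup analyses. It closes the paragraph on baseline-factor and age subgroups, and switching is a post-baseline event. Whether it covers the switching analysis is not clear.

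**The concern.** A question about preference and switching has as its null that the two are unrelated. That calls for a comparison between patients who switched and patients who did not. McNemar's test within each group asks something else, namely whether FCT and DT are equally liked in that group. Three problems follow.

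- **No comparison.** Two separate tests give no estimate or test of the difference between groups. With a large non-switcher group and a small switcher group, one test may be significant and the other not, only because of their sizes.
- **Pooled directions.** If patients tend to prefer the formulation they moved to, the two kinds of switcher favour opposite formulations. Their answers then offset each other in McNemar's statistic.
- **Timing.** The analysed preference is the Week 48 answer, given after the switch. It cannot show that preference influenced switching.

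At stake is the reading of one supportive analysis. A reader could see a link that is not there, or miss a strong one.

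**Working it through.** **Inputs from the documents (SAP 3):** 130 evaluable patients at Week 48; FCT 45%, DT 25%, no preference 30%; the test is "at a two sided significance level of 0.05 using McNemar's test for matched pairs".

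**Assumed, because the documents give no figure:** the share of patients who switch (5% to 30%), the direction split, and the strength of any link.

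**Step 1. The plan's own sample size.** With discordant share 0.45 + 0.25 = 0.70 and difference 0.20:

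n = (z0.975 + z0.80)² × (0.70 − 0.20²) / 0.20² = (1.960 + 0.842)² × 0.66 / 0.04 = 129.5, so 130.

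Allowing 10% missing: 130 / 0.9 = 144.4, so 145. Both figures reproduce.

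**Step 2. No link between preference and switching.** Both groups have 45/25/30. Let a be the probability that the exact McNemar test is significant in switchers and b the same in non-switchers, from the multinomial distribution. Exactly one test is significant with probability a(1 − b) + b(1 − a).

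| Switchers / non-switchers | a | b | Tests disagree |
|---|---|---|---|
| 6 / 124 (5%) | 0.9% | 73.3% | 72.9% |
| 13 / 117 (10%) | 7.4% | 70.5% | 67.4% |
| 20 / 110 (15%) | 12.1% | 67.6% | 63.3% |
| 26 / 104 (20%) | 17.0% | 65.1% | 60.0% |
| 39 / 91 (30%) | 24.9% | 59.0% | 54.5% |

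Preference is identical in the two groups here, so the disagreement reflects group size alone. Fisher's test of FCT versus DT preference by switch status (yes or no) gives a false signal in about 2% to 4% of trials over the same range.

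**Step 3. Strong link, 20 switchers.** In each direction, 80% prefer the formulation they moved to, 10% the other and 10% neither. With k DT-to-FCT switchers, the expected counts in the pooled group are:

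FCT = 0.8k + 0.1(20 − k); DT = 0.1k + 0.8(20 − k).

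| DT-to-FCT : FCT-to-DT | Expected FCT : DT | Pooled exact McNemar rejects |
|---|---|---|
| 10:10 | 9.0 : 9.0 | 0.2% |
| 12:8 | 10.4 : 7.6 | about 1% |
| 14:6 | 11.8 : 6.2 | 11% |
| 16:4 | 13.2 : 4.8 | 43% |
| 18:2 | 14.6 : 3.4 | 79% |

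At 10:10, Fisher's test of preference by switch direction rejects in 93% of trials.

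**Step 4. Which comparison would work.** At 10:10, with the other 110 patients at 45/25/30, comparing all switchers with non-switchers still pools the directions and rejects in only about 10% of trials. A three-group test (none, DT-to-FCT, FCT-to-DT) rejects in about 96%. The direction split is therefore needed, and a between-group test alone is not enough.

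**The case against.** The strongest reply is that this is a robustness check, as the opening of SAP 2.5.4 says. Asking whether FCT preference holds in patients who followed the planned sequence is sensible, and rerunning the primary analysis in non-switchers does that properly. This stands. Protocol 10.4.4 states no aim about preference and switching, so the mismatch between aim and method lies in the SAP only.

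Second, a reader might infer that the analysis will signal a false link. The documents do not support that. The sentence ruling out subgroup p-values may cover switching, in which case there are no conflicting verdicts to misread. Nor does either document say that one significant and one non-significant result is to be taken as evidence of a link. Step 2 shows what could mislead if both p-values are printed. It is not the error rate of a planned decision rule.

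Third, a reader might infer that the analysis must hide a strong link. It need not: masking is nearly complete only when the directions are close to balance, and it fades as one direction dominates. Protocol 4.2 also ties switching to investigator discretion and to adverse events of grade 2 or more, so switching need not follow preference.

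Fourth, the descriptive summaries of switch reasons and of the next-visit questionnaire give some information nearer the switch. They help, but neither compares switchers with non-switchers or estimates an association with Week 48 preference.

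None of this removes the core. The SAP states a specific question, and the prescribed method does not compare the groups, separate the directions or respect the time order.

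**Conclusion.** The point holds for the SAP as a mismatch between a stated aim and the method. Followed exactly, SAP 2.5.4 cannot identify an impact of preference on switching. At most, data of this kind could show an association.

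The consequences are conditional. With 130 evaluable patients, 5% to 30% switching, no link and both p-values shown, the two tests disagree in 54% to 73% of trials. With 20 switchers and the 80/10/10 link, the pooled switcher test detects a departure in 0.2% to 79% of trials as the split moves from 10:10 to 18:2. The analysis can mislead and can mask; how likely either is cannot be settled from the documents.

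A reader might go further and doubt the primary result. Nothing here supports that: the primary estimate, test and sample size are untouched. The priority is minor.

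**What to change.** In SAP 2.5.4:

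1. Reword the aim as the association between switching and Week 48 preference.
2. Tabulate the Week 48 answer (FCT, DT, no preference) by switch status: none, DT-to-FCT, FCT-to-DT.
3. For each switch direction, report the difference from non-switchers in the proportion preferring FCT, with an exact 95% CI, and give one exact test across the three switch groups.
4. Keep the non-switcher rerun of the primary analysis as a robustness display. Show the separate switcher result as estimates with CIs and no p-value, and state whether the rule against subgroup p-values covers this analysis.
5. Record the change in SAP section 4, which now lists none, because Protocol 10.4.4 commits to the separate primary analyses.

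The cost is SAP wording, one table and the section 4 entry. No new data are needed: Protocol 4.2 has the switch and its rationale recorded in the CRF, and SAP 2.4.1 already uses the actual switch date. The drawback is small cells if few patients switch, which the exact intervals will show openly.

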## **2.6 Analysis of the key secondary objective**

Not applicable.

## **2.7 Analysis of secondary efficacy objective(s)**

Refer to [Table 1.2.1](#) of Section 1 for the list of secondary objectives.

### **2.7.1 Secondary endpoints**

All the secondary efficacy evaluation will be performed on FAS population.

Refer to [Table 1.2.1](#) of Section 1 for the list of secondary endpoints.

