10.1 Analysis sets

The following analysis sets will be used in this trial.

Enrolled Set

The Enrolled Set comprises of all patients enrolled in this study.

Full Analysis Set

The Full Analysis Set (FAS) comprises all patients to whom study treatment has been assigned and who received at least one dose of each study treatment (DT and FCT). Patients will be analyzed according to the treatment they have been assigned to.

Safety set

The Safety Set includes all patients who received at least one dose of either study treatment (DT or FCT), and at least one safety assessment on or after Day 1.

Patients will be analyzed according to the study treatment received, where treatment received is defined as the assigned treatment if the patient took at least one dose of that treatment or the first treatment received if the assigned treatment was never received.

Per-Protocol set

The Per-Protocol Set (PPS) consists of a subset of the patients in the FAS who are compliant with requirements of the CSP (clinical study protocol) without any major protocol deviation.

The major protocol deviations that will lead to exclusion of patients from the PPS will be detailed in the SAP.

Pharmacokinetic analysis set

Not applicable

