10.5 Secondary objectives

The secondary objectives and endpoints are described in protocol [Section 3](#). The analyses will be based on FAS population.

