**Table 1.2.1: Study objectives and related endpoints**

| Objective   | Endpoint  |
|---|---|
| Primary  |   |
| To evaluate patient preference between deferasirox FCT and deferasirox DT | Proportion of patients claimed preference of deferasirox FCT over deferasirox DT as measured by preference questionnaire at Week 48 |

| Objective   | Endpoint   |
|---|--|
| Secondary  |  |
| To evaluate patient preference of deferasirox FCT or deferasirox DT or previous iron chelation                                      | Proportion of patients claimed preference of deferasirox FCT, deferasirox DT, and previous iron chelation as measured by preference questionnaire at Week 28   |
| To evaluate patient preference of deferasirox DT or previous iron chelation   | Proportion of patients claimed preference of deferasirox DT, over previous iron chelation as measured by preference questionnaire at Week 4 and Week 24  |
| To evaluate the reason behind preference for deferasirox FCT or deferasirox DT  | Proportion of preference reasons for deferasirox FCT over deferasirox DT as measured by preference questionnaire at Week 28 and Week 48  |
| To evaluate the effect of deferasirox FCT compared with deferasirox DT on patient compliance using pill count                       | Relative consumed pill count during deferasirox FCT (Week 25 to 48) compared with deferasirox DT (Baseline day 1 to Week 24)   |
| To evaluate the effect of deferasirox FCT compared with deferasirox DT or previous iron chelation on patient palatability using PRO | Absolute and relative change in domain scores of palatability questionnaire over time during deferasirox FCT (Week 28 to 48) compared with deferasirox DT (Week 4 to 24) or previous iron chelation (Screening)      |
| To evaluate the effect of deferasirox FCT compared with deferasirox DT or previous iron chelation on patient satisfaction using PRO | Absolute and relative change in domain scores of SICT questionnaire over time during deferasirox FCT (Week 28 to 48) compared with deferasirox DT (Week 4 to 24) or previous iron chelation (Screening)              |
| To evaluate the effect of deferasirox FCT compared with deferasirox DT or previous iron chelation on patient GI symptom using PRO   | Absolute and relative change in domain scores of SICT questionnaire over time during deferasirox FCT (Week 28 to 48) compared with deferasirox DT (Week 4 to 24) or previous iron chelation (Screening)              |

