## 2.2 Analysis sets

The following analysis sets will be used in this study.

**Enrolled Set:** The Enrolled Set comprises all patients enrolled in this study. Patients who discontinued from the study due to ineligibility immediately after Visit 2 are not considered as enrolled.

**Full Analysis Set (FAS):** The Full Analysis Set comprises all patients to whom study treatment has been assigned and who received at least one dose of each study treatment (DT and FCT). Patients will be analyzed according to the treatment they have been assigned to.

**Safety Set (SAF):** The Safety Set includes all patients who received at least one dose of either study treatment (DT or FCT), and at least one safety assessment on or after Day 1.

Patients will be analyzed according to the study treatment received, where treatment received is defined as the assigned treatment if the patient took at least one dose of that treatment or the first treatment received if the assigned treatment was never received.

**Per-Protocol Set (PPS):** The Per-Protocol Set consists of a subset of the patients in FAS who are compliant with requirements of the clinical study protocol (CSP) without any major protocol deviation.

Any major protocol deviation will lead to exclusion of patients from PPS. The list of PDs is defined in [Section 5.5](#).

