### **Patient preference of DT and iron chelation at Week 4 and Week 24**

The proportion and percentage (%) of patients including 95% CI will be reported separately for preference and non-preference of DT over iron chelation at Week 4 and Week 24. Exact and asymptotic p-values of Mc Nemar's test will also be presented as analogous to primary analysis, described in Section 2.5.2. The OR of patient preference (i.e.  $OR=p_{12}/p_{21}$ ), 95% CI and p-values will also be presented. Only patients who are pre-treated with iron-chelation will be considered.

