**Compliance using pill count**

Compliance is measured by pill/tablet count based on amount of medication dispensed, returned and reported as lost/wasted by the patient or caregiver. Compliance will be calculated for each treatment (FCT: Week 25- Week 48, DT: Baseline day 1 – Week 24) as the ratio of total count consumed to total count prescribed, where total count consumed is derived from cumulative dispensed, returned and lost/wasted counts and total count prescribed is the cumulative prescribed count.

The prescribed count corresponds to the count prescribed by the investigator for a period that the patient should have taken during this period. For each strength (125 mg, 250 mg and 500 mg tablets for Deferasirox DT; 90 mg, 180 mg and 360 mg tablets for Deferasirox FCT), the prescribed count for a period is calculated from the daily prescribed count at the beginning of this period multiplied by the duration (days) of this period. The daily prescribed count is the sum of counts prescribed per strength. The duration of a period will be calculated as (end date of the period) – (start date of the period) + 1. The following period duration calculation will exclude the start day. The total count prescribed is the sum of counts prescribed over all periods.

If a patient does not return the study drug, the compliance will not be calculated.

Analysis of covariance (ANCOVA) will be performed for comparison between both treatment groups (FCT and DT). The ANCOVA model for compliance endpoint will include treatment group and age group (2 to < 6 years, 6 to < 10 years, 10 to < 18 years, and  $\geq$  18 years) and thalassemia transfusion dependence (TDT and NTDT) as factors. Least squares estimates, 95% CI and p-value will be presented for each treatment and difference between treatments.

Summary statistics of number of pills (and percentages) will also be presented overall and by treatment and subgroups.

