## **2.11 Patient-reported outcomes**

The following PROs will be summarized using FAS.

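### DT-period secondary results leave out patients who stop DT without ever taking FCT, which may favour DT, chiefly in the Week 4 results and DT compliance

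*SAP*

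**What the plan says.** SAP section 2.7.1 assigns one analysis set to every secondary efficacy endpoint: "All the secondary efficacy evaluation will be performed on FAS population". SAP section 2.11 does the same for the questionnaires: "The following PROs will be summarized using FAS". Protocol section 10.5 agrees: "The analyses will be based on FAS population".

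SAP section 2.2 limits that set to patients "who received at least one dose of each study treatment (DT and FCT"); Protocol section 10.1 has the same condition. Footnote 5 of Protocol Table 7-1 places the first FCT dose on day 1 of Week 25.

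Several of these endpoints are measured on DT, before FCT is due:

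- Preference against earlier treatment (SAP Table 1.2.1): "Proportion of patients claimed preference of deferasirox DT, over previous iron chelation as measured by preference questionnaire at Week 4 and Week 24". SAP section 2.7.2 restricts it further: "Only patients who are pre-treated with iron-chelation will be considered".
- Palatability, mSICT and GI symptoms at Weeks 4 and 24 (SAP section 2.11).
- Pill-count compliance, whose DT window in SAP section 2.7.2 is "DT: Baseline day 1 – Week 24".

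**The concern.** Membership of the FAS depends on an event, the first FCT dose, that normally comes about 20 weeks after the Week 4 questionnaire. A pre-treated patient who answers at Week 4, stops DT at Week 16 and never takes FCT has a valid Week 4 answer and, if drug was returned, a DT pill count. Neither enters the planned tables.

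The loss need not be random. Protocol section 7.1.3.1 lists adverse events, insufficient effect, unacceptable toxicity and unwillingness to comply among the reasons for withdrawal. Patients leaving for such reasons may like DT less or take less of it. What is at stake is how DT compares with previous chelation at Week 4, and how DT compares with FCT on compliance. SAP section 2.7.2 plans no formal testing of secondary endpoints but presents p-values for both comparisons, so readers will draw conclusions from them.

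**Working it through.** **Step 1: who is outside the FAS.** A patient who takes DT and never takes FCT fails the both-doses condition. A patient switched from DT to FCT during Period 1 (allowed by Protocol section 4.2) meets it and stays in. The loss is therefore confined to patients who stop without any FCT dose.

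**Step 2: which results lose data because of the FAS.**

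- *Week 4 preference and questionnaire scores:* the answers exist and are dropped.
- *DT compliance:* this is a cumulative ratio of tablets consumed to tablets prescribed and does not require attendance at Week 24. It is calculable whenever drug is returned (SAP section 2.7.2), and is dropped.
- *Week 24 preference and scores:* a patient who stopped earlier normally has no Week 24 answer in any set. The completion-visit column of Protocol Table 7-2 contains no questionnaire, and SAP section 2.7.3 allows no imputation except for ferritin. Only patients who answer at Week 24 and then never start FCT are lost through the FAS.
- *Ferritin:* the efficacy summary uses the FAS, but SAP section 2.8.3 also summarises ferritin by visit, and SAP section 2.8 puts that on the Safety Set, which needs a dose of either formulation.

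The PPS is a subset of the FAS, so it cannot show the effect of this selection.

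**Step 3: the plan's own figures.** The sample size reproduces with discordant proportions 0.45 and 0.25: (1.960 + 0.842)² × (0.70 − 0.20²) / 0.20² = 129.5, hence 130; and 130 / 0.9 = 144.4, hence 145. These figures concern Week 48 preference. The documents give no sample size, expected preference or number of pre-treated patients for DT against previous chelation, and no rate of stopping during DT.

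**Step 4: illustration under assumed inputs.** Take pre-treated patients who express a preference between DT and previous chelation at Week 4. Let q be the share who stop without an FCT dose, and let p_stay and p_stop be the percentages preferring DT among those who reach FCT and those who do not. The FAS reports p_stay. All DT-treated patients would give

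p_all = (1 − q) × p_stay + q × p_stop,

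so the FAS overstatement is q × (p_stay − p_stop). All inputs are assumed: p_stay = 60%, q from 5% to 20%, p_stop from 0% to 80%. Each cell shows p_all, then the overstatement in percentage points.

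| q | p_stop 0% | 20% | 40% | 60% | 80% |
|---|---|---|---|---|---|
| 5% | 57% (3) | 58% (2) | 59% (1) | 60% (0) | 61% (−1) |
| 10% | 54% (6) | 56% (4) | 58% (2) | 60% (0) | 62% (−2) |
| 20% | 48% (12) | 52% (8) | 56% (4) | 60% (0) | 64% (−4) |

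For q = 10% and p_stop = 20%: 0.9 × 60 + 0.1 × 20 = 56%. The odds of preferring DT fall from 60/40 = 1.50 to 56/44 = 1.27. With p_stop still 20%, they are 58/42 = 1.38 at q = 5% and 52/48 = 1.08 at q = 20%.

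If the 10% allowance for missing measurements were all stopping during DT, which is a further assumption, that would be 0.10 × 145 = 14.5 patients. The overstatement would then run from 0 to 6 points for p_stop between 60% and 0%.

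**The case against.** The strongest reply is that the plan gives many dissatisfied patients a way to stay in. Protocol sections 4.2 and 7.1.3.1 allow a switch to FCT instead of withdrawal, and adverse events and insufficient effect are not among the reasons that bar it. Several reasons that do bar it, such as pregnancy, loss to follow-up and administrative problems, need not relate to liking DT. This stands. It reduces the number lost and weakens any claim about direction, but patients who stop without switching are still dropped.

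Second, compliance and the questionnaire endpoints are defined partly as FCT against DT, for which a set exposed to both is defensible. This also stands, and is a reason to keep the FAS result. It does not cover Week 4 preference against previous chelation, which does not involve FCT. For compliance the FAS is uneven: a patient who stops soon after one FCT dose can count for FCT if drug is returned, while one who stops early on DT without FCT cannot count for DT. The FCT preference and questionnaire results need completed answers, so the same asymmetry should not be claimed there.

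Third, DT intake is partly covered elsewhere: SAP section 2.4.1 summarises the percentage of planned dose taken on the Safety Set. That helps, but it leaves DT intake described on two populations with no stated reason.

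A reader might go further and infer that everyone who gives up DT is removed, or that a wider set would repair the Week 24 results. Early switchers and the missing Week 24 answers contradict both.

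**Conclusion.** The point holds with limits. The FAS selects on an event after the measurement, and patients who stop DT without taking FCT are removed from Week 4 preference against previous chelation, Week 4 questionnaire scores and DT compliance. No analysis on a wider set is planned for these endpoints.

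This may favour DT. A reader might infer that DT will look better than it is; the documents do not establish that. In the illustration the overstatement runs from 0 to 12 points when stoppers prefer DT no more than stayers do, and it reverses by 1 to 4 points if 80% of stoppers preferred DT. These figures rest wholly on assumed stopping rates and preferences; the actual size cannot be computed from the documents.

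Nor do the documents support extending the point to the primary result, to safety or to ferritin as a whole. The Week 48 comparison properly concerns patients who have had both formulations, safety uses the Safety Set, and ferritin is summarised there too. The consequence is for secondary estimates and their interpretation, not for the primary error rate.

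**What to change.** Keep the FAS for the FCT-versus-DT preference comparisons. For Week 4 preference against previous chelation, the Week 24 answers that are available, the DT-period questionnaires and DT compliance, analyse all patients with at least one DT dose and the relevant assessment. Keep the restriction to pre-treated patients where it applies. Show the FAS result beside each, and report how many patients stopped before FCT and why.

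The cost is a change of SAP wording and a rerun of existing tables on a set close to the Safety Set, with no new data. The compliance model can be rerun as written, since its factors are treatment, age group and transfusion dependence, with no patient term. The downside is unequal Ns between the DT and FCT columns. The adjacent FAS result addresses this, and SAP section 2.8.3 already accepts period-specific numbers for laboratory baselines.
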